**Research Strategy And Feasibility:** We propose a three year, phase 2, randomized doubleblinded 8-week treatment trial of IN-OXT vs. placebo in 50 child and adolescent subjects (25 male and 25 female) aged 5 to 17 years with a diagnosis of PWS. PWS diagnosis will be confirmed by study team via patient interview and confirmation by patient's past medical records and genetic testing results. At the screening visit, patient will have the opportunity to learn about the study and seek clarification on any outstanding questions. If patient voluntarily agree to participate, study team will work with the patients to complete the informed consent and if applicable, assent. In addition, a psychiatric interview and medical history review will be conducted to screen the patient for eligibility. The study team will also review patient's concomitant medications, assess for patient condition with CGI-S and hyperphagia using the Hyperphagia Questionnaire-Clinical Trials (HQ-CT). If patient meets selection criteria, the study team will arrange on behalf of the patient for an out-patient Quest visit, at which time patient will be asked for a screening blood draw to provide information on CBC, BMP, LFT, IGF-1, thyroid panel, lipid panel, testosterone, estrogen, hemoglobin A1C, and for applicable patient, a urine pregnancy test. Once the screening blood work results are available and all results are within acceptable range, and patient is otherwise eligible, patient will be invited for an in person visit to clinic where additional assessments including a complete physical and neurological exam, intelligence test, interval health or medication change, and if applicable, repeat urine pregnancy test will be conducted. If patient continues to meet all study inclusion and exclusion criteria and agrees to continue with study participation, the study team will formally submit the patient for randomization. The randomization is done in a 1:1 placebo to oxytocin ratio and stratified for gender. The result is blinded to the study team and the process is performed by the study pharmacist at the Clinical Research Pharmacy using a computer generated randomization table. Patients will receive a supply of oxytocin spray bottle with each spray dispensing 4 IU, or a matching placebo. The participant will start with an initial dose of 2 sprays per nostril (4 sprays per day), or 16 IU/day IN-OXT or placebo. To allow for optimization for adverse events or lack of response, we allow for one downward titration to 12 IU (3 sprays per day), and one upward titration to 24 IU (6 sprays per day) at week 2. This will also allow us to examine the relationship between weight based dosing and treatment response. Syntocinon (synthetic intranasal oxytocin) and matched placebo made by Novartis will be used in this protocol. We have an IND for the use of IN-OXT in PWS (IND 121109).

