#### Titration Schedule:

Adverse events: Study physician will review with study participants regarding the nature,

duration and severity of noted adverse events. The study physician will make clinical judgements on the relationship between reported adverse events with study medication. If there is a high likelihood of adverse events being related drug effects, the subject will titrate down from 16 IU/day (4 sprays per day) to 12 IU/day (3 sprays per day) and will be reassessed in one week). At the next assessment the side effects and tolerability will again be reviewed by the PI and medical monitor. If the side effects have resolved, the subject will be titrated back up to 16 IU/day. If the side effects persist, the subject may continue on the 12 IU/day for another week; or will be discontinued from the study at the judgement of the PI. Subjects who do not receive the full dose by week four will be discontinued. Any subject who is discontinued from the study will be referred for continued medical follow up.

Lack of response: One upward titration will be allowed at week 2 to 24 IU/day (4 sprays per day) if study clinician, with consultation of the PI, determines that study subject experiences no response on hyperphagia via a categorical yes/no determination, and has no adverse events. In our current ongoing pilot study, and in [name]'s study, the initial hyperphagia response was observed at the week 1 and week 2 ratings.

**Instructions for Dosing:** Once the cap has been removed from the spray, the device should be held upright to the nostril and the actuator depressed. The patient should be in the sitting position and should be instructed to inhale gently through the nose while the actuator is being depressed. The head should be tilted back once the actuator is depressed to ensure that no fluid runs out of the nose. Parents may assist the child with dosing.

**Outcome Measures:** Project outcomes will be determined by changes in scores of parent and clinician rated measures from baseline to week 8 and comparisons of week 8 measures between active treatment and placebo groups. Assessments will be administered according to the schedule of events in **Table 2**.

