#### **Detailed Description of Analyses**

**Primary Analyses**: Analyses for Specific Aim (1): To compare IN-OXT vs. placebo with respect to improvement in the hyperphagia severity in children with PWS via improvement in scores on the Hyperphagia Questionnaire-Clinical Trials.

The primary analysis will evaluate the hypothesis that IN-OXT will decrease hyperphagia vs. placebo.

- 1. Response to treatment will be assessed in two ways:
  - a. The effects of IN-OXT on hyperphagia will be analyzed using an intent-totreat approach with the two-sample T-test or Wilcoxon rank sum tests to compare treatment groups at specific visits as well as linear mixed effects models to analyze the repeated measures and changes over time.
  - b. The proportion of responders in each treatment group will also be compared. Response will be defined as a 30% or greater decrease in food-seeking and eating behaviors from baseline on the Hyperphagia Questionnaire-Clinical Trials. Dropouts for clinical reasons will be coded as non- responders. Differences in the proportion of responders in each treatment group will be evaluated using the chi-square test and time to response will be assessed using survival analytic techniques.
  - c. All tests will be two-tailed with an alpha level of 0.05.

**Secondary Analyses:** Analyses for Specific Aims (2) through (8): To compare IN-OXT vs. placebo in children with PWS on change in:(2) Repetitive behaviors via scores on the Repetitive Behavior Scale – Revised (RBS-R) and Montefiore-Einstein Rigidity Scale-Revised (MERS-PWS)(3) Weight and body composition via impedance analysis. (4) Quality of Life Measures on the World Health Organization Quality of Life Scale (WHOQOL)(5) Clinical Global Impression Scale (CGI-I) (6) Salivary Oxytocin Concentration (7) Safety Analyses

IN-OXT and placebo groups will be compared to the above secondary measures will be analyzed using methods similar to those outlined above. Associations between outcome measures at a specific time point will be analyzed with the Spearman rank or Pearson correlation coefficient.

- 1. Secondary Aim (1) Repetitive Behaviors
  - *a.* The effects of treatment on frequency and severity of repetitive behaviors will be assessed by fitting linear mixed effects models to the data on the RBS-R scores. We hypothesize that IN- OXT will significantly reduce repetitive behaviors from baseline to endpoint compared to Placebo.

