#### Additional Analyses

 Sample size permitting, we will explore the potential for ethnicity-by-treatment interactions. If effects of minority status are found that might be clinically meaningful, even if not statistically significant, we will report these to guide future research. Please see the Planned Enrollment Table for the breakdown of anticipated percentages of children of each ethnicity that will be enrolled.

- 2. We will test for gender by treatment interactions.
- 3. We will explore IQ by treatment interactions.
- 4. We will explore for co-morbidity (e.g. Type 2 Diabetes, Hypogonadism etc.) by treatment interactions.
- 5. We will explore for weight based dosing by treatment interactions.

**Missing data:** In any clinical trial, some subjects will be lost to follow up or will miss study visits but the expected rate is low given that this is only an 8 week trial. Primary analysis will be based on available data at each time point. The advantage of the linear mixed effects approach is that it can handle data which are missing at random and measurement times which are not evenly spaced. However, when the missingness mechanism depends on unobserved information, i.e., non-ignorable, parameter estimates and resulting tests on hypotheses will be biased without further adjustment. Different approaches for handling missing data will be performed in this study. Multiple imputation will be applied if missing data rates are observed to differ across observed covariates. Regardless of the technique, characteristics of patients who are lost to follow-up will be compared to those that remain in the study to assess the degree of any selection bias, and sensitivity analyses will be performed to evaluate robustness of conclusions to the different missing data approaches.

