**Power Analysis: Sample size justification:** The target sample size for this Phase 2 trial is 25 patients per treatment group. The power for the study has been calculated to generate a detectable signal with the sample size of 50 subjects. With this sample size, the study will have 80% power to detect a minimum effect size of d= 0.8 standard deviations in the outcome measures between groups using a two-sample T-test and a two sided Type I error rate of 5%. The study is powered based on a conservative estimate from a heterogeneous population. We expect that in this homogeneous PWS population selected to match study drug to underlying mechanism, the true power will exceed the conservative estimate. This minimum detectable difference is smaller than the treatment effects observed in our previous studies of IN-OXT in adults with ASD, which demonstrated an effect size of d=1.2 on a social cognition measure (RMET) [3], and an effect size of d = 0.84 on a quality of life measure (WHOQOL) [3]. In addition, our previous study of a V1a antagonist in adults with ASD demonstrated an effect size of d=0.8 on a social cognition measure (ASR Lust) [80], and an effect size of d = 0.8 on an Eye Tracking measure (Biological Motion Preference) [90]. The above effect sizes observed in our pilot data were based on a heterogeneous sample of ASD patients characterized by over 100 known different genetic contributing factors. In the proposed trial, both males and females will be included, and any heterogeneity in outcomes due to gender may attenuate overall treatment differences. However, by selecting an orphan population (PWS) with a single unique genetic contribution, and selecting a treatment that matches the known molecular mechanism (IN-OXT), we expect that the treatment effects in this study will nevertheless be greater than the effects observed in earlier studies.

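### Response-driven titration confounds the weight-based dose question (exploratory aim 3) rather than making it answerable; the exposure needs a definition fixed at baseline

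*Combined protocol and SAP*

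**What the plan says.** The Research Strategy And Feasibility paragraph fixes the design: "The randomization is done in a 1:1 placebo to oxytocin ratio and stratified for gender", and "The participant will start with an initial dose of 2 sprays per nostril (4 sprays per day), or 16 IU/day IN-OXT or placebo". Patients are randomised to drug or placebo, not to a dose level, and the starting dose ignores body weight. The paragraph then describes one downward step to 12 IU and one upward step to 24 IU at week 2, and adds: "This will also allow us to examine the relationship between weight based dosing and treatment response".

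The Titration Schedule sets the triggers. The upward step is open when the study clinician, consulting the PI, "determines that study subject experiences no response on hyperphagia via a categorical yes/no determination" and there are no adverse events. The downward step follows adverse events judged likely to be drug-related, and a patient not on full dose by week four is discontinued. Neither rule is limited to one arm.

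The question itself is exploratory aim 3 in both statements of the Specific Aims. Its only analysis text is item 5 of Additional Analyses: "We will explore for weight based dosing by treatment interactions". The plan does not say whether dose means starting, final or average dose, what value placebo patients carry, or how outcome-driven titration or covariates are handled.

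**The concern.** A dose-response analysis needs dose to vary for reasons unrelated to outcome. Here the only variation that titration adds toward the higher dose comes from early outcome: a patient moves to 24 IU because hyperphagia had not improved by week 2. Week-2 and week-8 scores in the same child will be correlated, so the higher-dose group would be expected to do worse at week 8 even if the extra drug did nothing.

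The protocol names titration as what enables the analysis, which points the analyst to the titrated dose. The Specific Aims describe the trial as a source of preliminary data for Phase 3, and a dose finding of this kind could be carried forward as if it were pharmacology.

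**Working it through.** **The plan's own figure.** The Power Analysis gives "The target sample size for this Phase 2 trial is 25 patients per treatment group" and "80% power to detect a minimum effect size of d= 0.8 standard deviations in the outcome measures between groups"; the Detailed Description of Analyses adds "All tests will be two-tailed with an alpha level of 0.05". Normal approximation: power = Φ(0.8 × √(25/2) − 1.96) = Φ(2.828 − 1.960) = Φ(0.868) = 80.7%. The exact noncentral t (48 df) gives 79.1%, with a minimum detectable d of 0.81. The stated 80% is reproduced. It concerns the two-arm comparison; no figure is given for aim 3.

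**Inputs for the dose question.** From the documents: 25 per arm, 16 IU start, 24 IU after week-2 non-response, 40 lb minimum weight. Not in the documents, so assumed: week-2 non-response 20-60% (base 40%); week-2/week-8 correlation ρ 0.3-0.7 (base 0.5); log-normal weight, median 110 lb, log-SD 0.25-0.6 (base 0.45); treatment effect 0.8 SD.

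**How far apart the dose groups fall with no dose effect.** Let a fraction p be non-responders at week 2, with normal cut-point z. The expected week-8 gap between up-titrated and other active patients is −ρ × φ(z) / [p(1 − p)]. For p = 0.4, z = −0.253 and φ(z) = 0.386, so the gap is −ρ × 0.386/0.24 = −1.61ρ. That is −0.48, −0.81 and −1.13 SD for ρ = 0.3, 0.5 and 0.7. The simulations give the same values.

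**Final dose / weight, no true effect of the extra dose** (4,000 simulated trials per row; slopes in SD of improvement per 0.1 IU/lb; significantly negative should be 2.5%):

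| Scenario | Active-arm slope | Sig. negative | Interaction slope | Sig. negative |
|---|---|---|---|---|
| Base | −0.175 | 11.9% | −0.045 | 3.4% |
| ρ = 0.3 | −0.107 | 6.9% | −0.031 | 2.7% |
| ρ = 0.7 | −0.234 | 17.1% | −0.056 | 2.9% |
| 20% non-response | −0.147 | 8.8% | +0.024 | 2.1% |
| 60% non-response | −0.152 | 10.8% | −0.063 | 3.9% |
| Log-SD 0.25 | −0.431 | 21.8% | −0.092 | 3.6% |
| Log-SD 0.6 | −0.104 | 8.3% | −0.025 | 2.8% |
| ρ = 0.7, log-SD 0.25 | −0.597 | 40.1% | −0.117 | 3.9% |
| Starting dose / weight, base | +0.009 | 2.4% | +0.008 | 2.4% |

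**Two-sided false positives at nominal 5%**, for ρ 0.5-0.7, log-SD 0.25-0.5 and 31-50% of active patients up-titrated:
- active-arm Spearman correlation on final IU/lb: 9-44%;
- both-arm interaction on final IU/lb, placebo carrying its sham dose: 3.6-6.7%, the top value with 50% of active and 80% of placebo patients up-titrated;
- the same interaction when benefit from the drug varies between patients (assumed SD 0.8-1.2): about 5-17%, nearly all in the direction of harm;
- starting dose over baseline weight: about 4-7% in every scenario.

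The third line differs from the second for a structural reason. In the active arm, week-2 non-response picks out children who benefit less from the drug; sham titration on placebo cannot select on that, so the two artefacts no longer match.

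**Other forces on the active-arm slope** (base case). If heavier children improve less by 0.2 or 0.4 SD per SD of log weight, the slope becomes 0.00 or +0.22. If they improve more by 0.2, it becomes −0.32. A true benefit of 0.5 SD per 0.1 IU/lb of added dose gives −0.01: the benefit is hidden.

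The 12 IU step was not modelled. By the written rule a down-titrated patient returns to 16 IU or is discontinued, so few week-8 completers should be at 12 IU. The step adds selection on tolerability, of unknown direction.

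**The case against.** The strongest reply is that the one analysis named for this aim is a dose-by-treatment interaction, not an active-arm correlation. Titration is blinded and open to both arms, so placebo non-responders are sham-titrated by the same rule and carry a similar artefact. This stands for the simple null case, where the interaction stays close to its nominal level. It has two limits. The plan does not say that placebo patients carry a nominal dose, and the cancellation fails when drug response varies between patients. Nor do aim 3 and the Research Strategy sentence confine the question to the interaction.

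It can also be said that the aim is one exploratory line in a Phase 2 trial. That is so, and it limits the consequence.

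A reader might infer that a higher IU/lb is bound to look harmful. The documents do not support that. They leave the dose variable undefined; the interaction they name largely cancels the artefact; and most variation in IU/lb comes from body weight, which can offset or reverse the slope. Even in the active-arm analysis the null slope is negative in 69-97% of simulated trials, not all, and a true benefit of the size tried is masked rather than reversed. A reader might also infer that the primary result is compromised. It is not: the arms are compared as randomised, and titration is part of both regimens.

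**Conclusion.** The stated rationale is wrong: titration does not make the weight-based dose question answerable, because dose above 16 IU/day follows early non-response. If final dose is used within the active arm, the analysis is biased toward apparent harm, with about 9-44% false positives under no dose effect. In the both-arm interaction with nominal placebo doses the excess is small, unless drug response varies between patients, when it is about 5-17%. That the titrated dose follows early outcome comes from the protocol's own rules. The direction and size of the bias rest on assumed non-response, correlation, weight spread and response variability, so the percentages show scale and do not predict this trial. The point is a modest one about an exploratory aim, worth correcting because the correction is nearly free.

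**What to change.** Wording only, with no change to dosing or titration rules:

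1. In Research Strategy And Feasibility, delete the sentence saying that titration allows the dose-response relationship to be examined.
2. In exploratory aim 3 (both statements) and Additional Analyses item 5, define exposure as assigned starting dose divided by baseline weight. Baseline weight is already in the Schedule of Events.
3. Test it as an interaction with treatment across both arms, giving placebo patients their nominal value, adjusted for age and baseline HQ-CT.
4. State that, with one starting dose, this variable is inverse body weight. The result therefore cannot separate dose from weight and is not causal; adjustment does not cure that.
5. Report titrated-dose summaries by arm descriptively, without tests. Before they are tabulated, reconcile the number of sprays given for 24 IU/day, which is six in Research Strategy And Feasibility and four in the Titration Schedule.

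The cost is a narrower aim: whether the treatment effect varies with starting IU/lb, not whether more drug works better. Sample size, power and the primary analysis do not change.

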#### **Inclusion Criteria:**

- 1. Male or female pediatric outpatients aged 5 to 17 years.
- 2. Must be in PWS nutritional phase 2b or 3 as determined by PI.
- 3. Must be on growth hormone treatment and have been receiving stable dose of growth hormone treatment for at least three months prior to screening date. Treatment cannot have been interrupted for more than one week within 3 months of screening.
- 4. Diagnosis of PWS confirmed by exam, genetic testing and patient medical records.
- 5. A score of at least moderate severity on the Hyperphagia Questionnaire-CT at both screening and baseline visits
- 6. Stable dosages of hormone treatments (including testosterone and estrogen supplements) for 4 weeks prior to randomization and for the duration of the study.
- 7. Stable dosages of metabolic treatments that could affect appetite (including metformin)

for 4 weeks prior to randomization and for the duration of the study.

- 8. Stable pharmacologic, educational, behavioral and/or dietary interventions for 4 weeks prior to randomization and for the duration of the study.
- 9. Physical exam and laboratory results that are within the normal range for individuals with PWS.
- 10. Presence of a parent/caregiver/guardian that is able to consent for their participation and complete assessments regarding the child's development and behavioral change throughout the study.

#### Exclusion Criteria:

- 1. Exposure to any investigational agent in the 30 days prior to randomization
- 2. Child not receiving growth hormone treatment.
- 3. Children weighing less than 40 lbs.
- 4. Children with unstable Type 2 Diabetes confirmed by Hemoglobin A1C level >=6.5% at screening.
- 5. Children with unstable medical co-morbidities at baseline.
- 6. Children with active upper respiratory infections at screening.
- 7. A primary psychiatric diagnosis other than ASD, including bipolar disorder, psychosis, schizophrenia, PTSD or MDD. These patients will be excluded due to potential confounding results.
- 8. Pregnant or lactating patients or patients who will not agree to use a double barrier method of contraception. IN-OXT has not been studied in pregnant or lactating women.
- 9. Females using an estrogen-based contraceptive. As an alternative to an estrogen based contraceptive, subjects will be counseled to use progesterone-based contraceptives; cervical caps; cervical sponges; or spermicidal foam in combination with a condom. Subjects will need to use a double barrier method to be in the study.
- 10. A medical condition that might interfere with the conduct of the study, confound interpretation of study results or endanger the subject's well-being.
- 11. A known diagnosis of Rett's Syndrome or Childhood Disintegrative Disorder or marked sensory impairment such as deafness or blindness.
- 12. Subjects who have had changes in allied health therapies, behavioral or educational interventions within four weeks prior to randomization other than those associated with school holidays.
- 13. Subjects who have had changes in medications or medication doses of risperidone, aripiprazole, other antipsychotic medications, clonidine, guanfacine, stimulants or anticonvulsants within four weeks of randomization.

**Titration Plan and Schedule:** If side effects occur, the medical monitor, PI and co-I's will determine if and when to titrate based on severity of the adverse event and relation to the study drug. If there is a significant exacerbation of known PWS co-morbidities, including Type 2 diabetes, sleep apnea or hypogonadism, or any other adverse event rated by the study physician as severe, a clinical determination will be made by the medical monitor, PI and co-I's, as to the patient's eligibility to continue in the study, or to follow the titration schedule, as described below. Both co-investigators, [name] and [name], have extensive expertise in co-morbidities associated with PWS, as does consultant [name].

